12. STATISTICS

12.1 General Statistical Methods

This section outlines the general study design, study endpoints, and statistical analysis strategy for the study. If, after the study has begun, changes are made to primary and/or key secondary hypotheses, or the statistical methods related to those hypotheses, then the protocol will be amended (consistent with ICH Guideline E9). Changes to exploratory or nonconfirmatory analyses made after the protocol has been finalized, along with an explanation as to when and why they occurred, will be listed in the Clinical Study Report (CSR). Post hoc exploratory analyses will be clearly identified in the CSR. Full details will be in the Statistical Analysis Plan (SAP). Any deviations from the statistical plan will be described and justified in a protocol amendment and/or in the CSR.

All statistical analyses will be carried out using Statistical Analysis System (SAS) version 9.3 (or later). The SAP will be written and finalized prior to the first patient randomized. The SAP will provide a detailed and expanded description of the statistical methods outlined in this protocol. Additional analyses, such as in important subgroups, will be described.

The data from this study will serve a dual purpose:

- (i) To provide efficacy and safety data in the Overall Population, who receive study medication as 2nd to 5th line of therapy, for regulatory submissions in the EU and jurisdictions in which the 2nd line + eribulin label applies.
- (ii) To provide efficacy and safety data in the 3rd line + population who receive study medication as 3rd to 5th line of therapy, for regulatory submissions in the US and jurisdictions in which the 3rd line + eribulin label applies.

For the Overall Population, the critical efficacy endpoints shall be PFS and OS. The formal analysis of PFS is planned once 346 PFS events have accrued and is expected to be conducted when all randomized patients have been followed for a minimum of 12 months. At the time of the PFS analysis, an interim analysis of OS will be performed, and a final analysis of OS will take place once all randomized patients have been followed for a minimum of 24 months.

For the 3rd line + population, the critical efficacy endpoints shall be ORR, PFS, with ORR and PFS being co-primary efficacy endpoints. The formal analysis of ORR is planned when all such patients have been randomized and followed for a minimum of 6 months. The formal analysis of PFS will take place once 286 PFS events have accrued and is expected when all randomized patients have been followed for a minimum of 12 months; if the PFS in the 3rd line + population meets the allocated alpha level, PFS in the Overall Population will also be formally tested at the same alpha level; further, at the time of the PFS analysis an interim analysis of OS will be performed. The final analysis of OS will take place once all randomized patients have been followed for a minimum of 24 months.

In this study, the statistical design in the overall, 2nd line + population, with pre-defined alpha allocation and recycling, is such that if PFS does not meet statistical significance at its allocated alpha level, then the design still allows OS to be tested and, if it meets statistical significance at its allocated alpha level, then the study can still be formally positive for efficacy.

Similarly, the statistical design in the overall, 3rd line + population, even if ORR does not meet statistical significance at its allocated alpha level then PFS can still be tested and, if it meets

Sponsor Logo/Name: Polyphor Ltd

Protocol No.: POL6326-009

Version 3.0

statistical significance at its allocated alpha level, the study can still meet its primary objective. Further, if PFS does not meet statistical significance at its allocated alpha level, then OS can still be tested and, if it meets statistical significance at its allocated alpha level, then the study can still be formally positive for efficacy.

Alpha allocation and recycling will ensure control of the overall Type I error rate within each of (i) the Overall Population and (ii) 3rd line + population.

Analyses of biomarkers will be addressed in a separate analysis plan.

12.2 Overall Population Efficacy Analysis Plan relevant to the EU and other jurisdictions in which the 2nd line + Eribulin Label applies

12.2.1 Sample Size

Assuming a median PFS on eribulin of 3.9 months, to test for a hazard ratio versus balixafortide + eribulin of 0.699 (corresponding to a median PFS of 5.6 months), a total of 346 PFS events are required to provide 90% power at the 1-sided 2.0% alpha level. Equally, 346 PFS events provides 94.6% power for a hazard ratio of 0.674, corresponding to a PFS of 5.8 months. Assuming a 12-month recruitment period (η =2; Carroll, 2009(3)) and a minimum 12-month follow-up period after the last patient is randomized, a total of 384 patients will be recruited. Patients who discontinue from the study will not be replaced.

12.2.2 Analysis Sets

The following analysis sets are defined for the Overall Population:

- Intention-to-treat (ITT) Population is defined as all randomized patients. Efficacy data in this population will be summarized by randomized treatment. The co-primary endpoint PFS and key secondary efficacy endpoint OS will use the ITT population. Patients will be analyzed by the treatment arm to which they are randomized.
- **Safety Population** is defined as all randomized patients who receive at least one dose (or partial dose) of study medication. Patients will be analyzed by the treatment arm received, based on the first dose of study drug.
- Response Evaluable Population will be used to evaluate disease response. The Response Evaluable Population includes all patients who are randomized in the study with measurable disease by RECIST v1.1 (as determined by the Investigator). The coprimary endpoint analysis of ORR and other secondary endpoint analyses of CBR and duration of response will be conducted using the Response Evaluable Population. Patients will be analyzed by the treatment arm to which they are randomized.
- Patient Reported Outcome (PRO) Population is defined as all patients in the ITT Population where the patient has at least one post randomization PRO value. Patients will be analyzed by the treatment arm to which they are randomized.

12.2.3 Demographics and other Baseline Characteristics

The following demographic and baseline disease characteristic data for all analysis populations will be summarized: age (years), sex, race, ethnicity, ECOG performance status, reproductive status, smoking history, height (cm), weight (kg), body surface area (m²), systolic BP (mmHg), and diastolic BP (mmHg). Key laboratory parameters will also be summarized.

Date: 15 July 2019

Protocol No.: POL6326-009

Version 3.0

12.2.3.1 Medical History

Medical history of BC will be summarized for the ITT population. Medical history will include time since initial diagnosis (years), time since diagnosis of locally recurrent or metastatic disease (years), stage at initial diagnosis, TNM staging, receptor data, receptor status, and pathological diagnosis.

Medical conditions collected at Screening will be mapped by the latest version of Medical Dictionary for Regulatory Activities (MedDRA) and will be summarized by System Organ Class (SOC) and preferred term (PT) for the ITT population. For summary tables, a patient will be counted only once per body system and PT.

Patients will be stratified according to:

- Line of therapy (2nd line versus 3rd line +) for locally recurrent or metastatic BC.
- HR status (positive versus negative) based on ER or PgR status.
- CDK 4/6 inhibitor treatment received previously (received a CDK 4/6 inhibitor previously versus not received a CDK 4/6 inhibitor previously).
- Visceral versus non-visceral disease. Visceral metastases will include brain, pulmonary, pleural, hepatic and peritoneal involvement (including pleural effusions and ascites). Any other sites of metastases (e.g. bone, lymph nodes, and skin) will be considered to be non-visceral. Patients with visceral metastases, irrespective of the presence of any other metastatic sites (e.g. bone), will be categorized as visceral. All other patients without visceral metastases will be categorized as non-visceral.

12.2.3.2 Medical History of Prior Systemic Cancer/Oncology Therapies

The number and percent of patients receiving prior anthracycline and/or a taxane will be summarized. The number of prior hormonal therapies, cytotoxic chemotherapy regimens for BC, neoadjuvant regimens, adjuvant regimens, cytotoxic regimens for locally recurrent, and cytotoxic regimens for metastatic disease will be calculated based on prior cancer therapies reported on eCRFs and summarized for the ITT population.

Duration of prior anthracycline and/or taxane use will be summarized descriptively. If a patient received multiple treatments of a therapy, the sum of duration will be calculated.

Prior systemic cancer/oncology therapies will be tabulated for the ITT population using the latest version of World Health Organization Drug Dictionary Enhanced (WHO-DDE) and Anatomical, Therapeutic, or Chemical (ATC) level 2 classifications and PT.

12.2.3.3 Previous Radiotherapy and Surgical History

Previous radiotherapy and surgical history related to BC will be listed for the ITT population.

Surgical history related to BC and the percentage of patients receiving prior radiotherapy will be summarized for the ITT population.

12.2.4 Patient Disposition

A summary of patient disposition will display the number of patients who were randomized and who comprised each analysis population by treatment arm. In addition, the number of patients who discontinued study medication, and the number of patients who discontinued Sponsor Logo/Name: Polyphor Ltd

Protocol No.: POL6326-009

Version 3.0

from study, both overall and by reason, will be presented by randomized treatment arm. Disposition data, including populations to/from which patients are included/excluded, will be presented graphically.

The three randomization stratification factors, HR status, previous CDK 4/6 inhibitor treatment, and visceral disease, will be listed and tabulated as documented on the eCRF and as recorded by randomized treatment arm. Any discrepancies between those two sources will be identified and summarized.

12.2.5 Protocol Deviations

Details on the handling of protocol deviations will be described in a separate Deviations Plan.

Patients with important protocol deviations will be listed and summarized by treatment arm as randomized and for each study site. Important protocol deviations will include, but is not limited to, the following:

- Those who entered the study even though they did not satisfy the entry criteria.
- Those who developed withdrawal criteria during the study, but who were not withdrawn from the study medication.
- Those who received the wrong study medication or incorrect dose.
- Those who received a concomitant treatment that is prohibited or not recommended.

These important protocol deviations will be captured by searching relevant data fields reported in the clinical database. Final determination of important deviations will be made by the joint Polyphor/CRO study team prior to the first planned interim analysis and associated database lock. All protocol deviations that are captured will be summarized by category and type and will be presented in a data listing.

12.2.6 Treatments and Medication

12.2.6.1 Prior and Concomitant Medication

Prior and concomitant medications will be recorded on the source data and eCRF and coded to ATC code and preferred drug name using the latest version of WHO-DDE. Concomitant medications will be tabulated for the Safety Population by WHO-DDE ATC.

12.2.6.2 Subsequent Anti-cancer Therapy

Subsequent anti-cancer therapy will be summarized for the ITT Population. Subsequent anti-cancer therapy will be tabulated using the latest version of WHO-DDE and ATC Level-2 classifications and PT.

12.2.6.3 Exposure/Study Medication

Overall exposure to study medications, and study medication administration for each cycle and all cycles combined will be summarized for the Safety Population. Overall exposure to study medication will be summarized in terms of exposure duration and cumulative number of cycles.

254

Date: 15 July 2019

Protocol No.: POL6326-009

Version 3.0

12.2.7 Efficacy Analyses

12.2.7.1 Primary Endpoint: Progression Free Survival

PFS time (defined as the time from randomization to the first progression or death, as judged by an IRC) is the primary endpoint. The alpha allocation will be 0.040 2-sided. PFS will be analyzed via Cox regression modelling in the ITT population. Patients free from progression and death will be censored at their last follow-up visit. The analysis will be stratified for randomization stratification factors and a fixed effect term will be included for randomized treatment. The hazard ratio will be estimated from the model along with the associated 96% confidence interval (CI) and 2-sided p-value. The data will also be displayed using Kaplan-Meier curves and median PFS times will be estimated.

Supportive analyses for PFS will be conducted using:

- (i) A stratified log rank test on PFS as determined by IRC; strata will be the randomization stratification factors. The 2-sided p-value will be extracted and presented alongside the results of the Cox analysis; and
- (ii) Cox regression analysis on PFS as determined by the local Investigator's review.

12.2.7.2 Key Secondary Endpoint: Overall survival

OS will be analyzed using the same Cox model as for PFS. The CI coverage for OS at the planned interim and at the final analysis will be determined by the allocated alpha level. A sensitivity analysis using a stratified log rank test will be performed, again as per the analysis of PFS.

The OS proportion at 6, 12 and 18 months, including 95% Cls, will also be presented.

12.2.7.3 Type I Error Control

[figure not shown]
The formal analysis of PFS is planned for the Overall Population once 346 PFS events have accrued and is expected when all randomized patients have been followed for a minimum of 12 months. An interim analysis of OS will take place at the same time, and the final analysis of OS will take place once all randomized patients have been followed for a further 12 months (i.e. a minimum of 24 months).

The overall Type I error rate will be controlled at 5% across the primary and key secondary endpoint analyses by means of alpha allocation and recycling as described in Figure 2.

Protocol No.: POL6326-009

Version 3.0

Figure 2 Type I Error Control for Primary and Secondary Efficacy Analyses in the Overall Population

OS: overall survival; PFS: progression free survival.

12.2.7.4 Other Secondary Endpoints

Analysis of the other secondary endpoints in the overall, 2nd line + population, i.e. ORR, CBR, DCR, time to response, and duration of response will not be subject to Type I error control. Statistical tests will be 2-sided with a nominal Type I error rate of 0.05.

ORR will be analyzed by exact logistic regression and be stratified for randomization stratification factors. The odds ratio will be estimated from the model along with the associated 95% CI and 2-sided p-value. Exact Clopper-Pearson 2-sided 95% CI limits will be calculated for the proportion of patients with ORR in each arm.

ORR analyses will be performed for the Response Evaluable Population. Patients who do not have measurable disease at baseline will be excluded from the population. In addition to presenting ORR, the best response using response categories CR, PR, SD, PD, and not evaluable (NE) will be tabulated. The proportion of the response in each response category will be calculated. Patients who do not have any post-baseline tumor assessment will be counted under the category NE. SD requires at least one post-baseline scan performed at 6 weeks (42 days) or later. Patients who did not have any post baseline scans for the 6 week assessment or later, and who also do not have a documented PD will be counted as NE.

Duration of response will be analyzed in the Response Evaluable Population, and CBR will be analyzed in both the Response Evaluable Population and ITT population.

CBR will be compared between the treatment arms using exact logistic regression as described for ORR. Exact Clopper Pearson 2-sided 95% confidence limits will be calculated for the CBR of each treatment arm.

Duration of response will be analyzed via Cox regression modelling with a fixed effect term for randomized treatment. The hazard ratio will be estimated from the model along with the associated 95% CI and 2-sided p-value. The data will also be displayed using Kaplan-Meier curves; median duration of response and the 95% CIs will be estimated from the Kaplan-Meier

Protocol No.: POL6326-009

Version 3.0

by treatment arm. A supportive analysis will be performed based on the expected duration of response as per Ellis et al (2008) (59).

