8.2 Tumor Assessments

The Study Schedule of Assessments and sampling are outlined in Section 1.1. Since the primary endpoint of the study is PFS, it is critical that tumor assessments are performed according to the Study Schedule in a timely and complete manner to allow full comparability of the two treatment arms. To prevent the introduction of any bias into the efficacy results, the assessment must be performed according to the calendar regardless of any dosing delay or interruption. Imaging assessments will be scheduled using the randomization date as the reference date for all timepoints and NOT scheduled according to the date of the previous imaging timepoint. A delay in the imaging assessment to accommodate a treatment delay is not permitted. Incomplete assessment and/or wrong timing (out of Schedule) will result in the inability to accurately assess disease status for that timepoint. CT/MRI scan will be used to measure target lesions that are selected for response assessment. For a given patient/tumor lesion, the same technique for tumor assessment MUST be used throughout the study.

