8.2.2 Post-baseline Tumor Assessments

Tumor assessments are to be scheduled using the randomization date as the reference date for all timepoints; tumor assessments are NOT to be scheduled according to the timepoint of the previous tumor assessment.

Protocol No.: POL6326-009

Version 3.0

From the date of randomization, patients will be evaluated according to RECIST v1.1 for CR, PR, SD, or PD based on CT/MRI scans performed every 6 weeks (±7 days) during the first year, and then every 12 weeks (±7 days), thereafter, until PD is documented by RECIST v1.1. The RECIST v1.1 definitions of the criteria used to determine tumor response for target lesions are provided in Table 5 and for non-target lesions in Table 6. Table 7 provides a summary of the overall response calculation that is to be used at each response assessment timepoint specified in the Study Schedule for patients who have measurable disease at baseline. When patients have non-measurable disease only, Table 8 is to be used. Further information is summarized in Appendix 3 Summary of RECIST v1.1 Guidelines.

Table 5 Determination of Objective Tumor Response for Target Lesions

Tumor Response	Evaluation of Target Lesions
Complete Response (CR)	Disappearance of all target lesions. Any pathological lymph nodes (whether target or non-target) must have reduction in short axis to <10 mm.
Partial Response (PR)	At least a 30% decrease in the sum of diameters of target lesions, taking as reference the baseline sum diameters.
Progressive Disease (PD)	At least a 20% increase in the sum of diameters of target lesions, taking as reference the smallest sum of diameters of target lesions recorded on study (this includes the baseline sum if that is the smallest on study). In addition to the relative increase of 20%, the sum must also demonstrate an absolute increase of at least 5 mm. (Note: the appearance of one or more new lesions is also considered progression).
Stable Disease (SD)	Neither sufficient shrinkage to qualify for PR nor sufficient increase to qualify for PD, taking as reference the smallest sum diameters while on study.

Source: (55)

Further details can be found in Appendix 3 Summary of RECIST v1.1 Guidelines.

Protocol No.: POL6326-009

Version 3.0

Table 6 Determination of Tumor Response for Non-target Lesions

Tumor Response	Evaluation of Non-target Lesions

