The data from protocol POL6326-009 will serve a dual purpose: (i) to provide efficacy and safety data in the 3^{rd} line+ patient population of patients with locally recurrent or metastatic breast cancer primarily for regulatory submissions in the US and jurisdictions in which the 3^{rd} line+ eribulin label applies and (ii) to provide efficacy and safety data in the overall population of patients who receive study treatment in the 2^{nd} line+ patient population, for regulatory submissions in the EU and jurisdictions in which the 2^{nd} line+ eribulin label applies.

This execution plan describes the analyses and data summaries in relation with the 3^{rd} line+ population.

2. Objectives

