The number of patients experiencing events and the number of censored patients will be summarized by randomized treatment arm with reasons for an event/censoring. The median survival times will be estimated by the Kaplan-Meier method and presented along with their corresponding 95% CI. The 25th percentile and 75th percentile for the survival times along with the corresponding 95% CI for the percentiles will also be displayed, CI will be calculated using method of Brookmeyer and Crowley (1982). Additionally, PFS probabilities at fixed time points i.e. 3, 6, 9, 12, 15 months will be derived from the Kaplan-Meier estimates with 95% confidence intervals, CI will be calculated using the Greenwood formula. The time points will be displayed based on the data availability.

Corresponding plots of Kaplan-Meier curves by treatment arm will also be presented. The plots will display the number of patients at risk every 3 months. Alongside this the PFS data will be presented in a listing by treatment arm.

Objective Response Rate

The ORR, defined from the best response as assessed by the IRC, will be analyzed by an exact logistic regression, stratified for randomization stratification factors excluding line of therapy (see Section 4.2 for further details). The odds ratio will be estimated from the model along with the associated 99.9% CI (0.001 alpha) and 2-sided p-value. Exact Clopper-Pearson 2-sided 95% confidence limits will be calculated for the proportion of patients with objective response in each arm.

ORR analyses will be performed for the RE (3rd line+) set and RE (3rd line+ Confirmed) set. Analysis of the RE (3rd line+ Confirmed) set is added as sensitivity and is not part of the alphacontrol for this study. In addition to presenting ORR, the best response as assessed by the IRC using response categories CR, PR, SD, PD and NE will be summarized. The number and percentage of patients in each response category will be presented by treatment arm. Patients who do not have any post-baseline tumor assessment will be counted under the category NE. SD requires at least one post-baseline scan performed at minimum of six (6) weeks (42 days) +/- seven (7) days, for a minimum time on-study of thirty-five (35) days or later. Patients who did not have any post baseline scans for the 6-week assessment or later and also do not have a documented PD will be counted as NE.

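### The protocol's day-42 minimum for stable disease ignores the ±7-day scan window and differs from the SAP's unlisted 35-day floor (minor)

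*Protocol*

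**What the plan says.** **Schedule.** Protocol 8.2.2 evaluates response "based on CT/MRI scans performed every 6 weeks (±7 days) during the first year". Protocol 8.2 adds that "Imaging assessments will be scheduled using the randomization date as the reference date for all timepoints", in both arms.

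**Protocol rule for SD.** Section 12.2.7.4, in the paragraph on ORR and best response, says "SD requires at least one post-baseline scan performed at 6 weeks (42 days) or later". The next sentence assigns NE differently. It covers "Patients who did not have any post baseline scans for the 6 week assessment or later" who also have no documented progression, so it refers to the visit and not to day 42.

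**Reach of that rule.** Protocol 12.3.7.1 (for ORR) and 12.3.7.4 (for the other secondary endpoints) analyze the 3rd line+ population as the Overall Population is analyzed.

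**SAP rule.** For the IRC assessment, SAP 8.1.3 says "SD requires at least one post-baseline scan performed at minimum of six (6) weeks (42 days) +/- seven (7) days". It then fixes the resulting floor at 35 days in the study. SAP Appendix 14.5 uses the same 35 days from randomization for investigator-assessed best response. The SAP restricts its scope to the 3rd line+ population. Its section 12, which sets out changes from the protocol and from an earlier SAP version, does not mention this one.

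**DCR.** Protocol 8.3.7 defines it with no minimum length of SD. SAP 8.4.4 accepts SD as best response whatever its length, while Appendix 14.5 allows SD as best response only from 35 days.

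**The concern.** The day-42 cut-off runs through the middle of the permitted window for the first scan, so a site that scans on day 38 has complied fully with the imaging schedule. If that scan shows SD and no further scan follows, the patient is not SD under one sentence. The patient has nevertheless had the 6-week assessment, so the NE sentence does not clearly apply either. The categories offered are CR, PR, SD, PD and NE, and none of them clearly fits.

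The two documents also give different minima for the same 3rd line+ patients. A programmer following the protocol and one following the SAP could produce different best-response tables, and nothing in SAP section 12 warns of it. If the minimum feeds DCR, that rate changes too.

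**Working it through.** **1. Reproduce the SAP floor.** 6 weeks × 7 = day 42. Less the 7-day window, 42 − 7 = day 35, which is the SAP figure. The on-time first scan therefore spans days 35 to 49 (15 days), and the second, 84 ± 7, spans days 77 to 91. Days 35 to 41 are 7 of the 15 days, or 46.7%.

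**2. Who can lose SD.** A patient still SD at the second scan is SD under either document. Only patients with an early on-time first scan and no later qualifying scan are affected. What counts as qualifying has two readings:

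- Literal: any post-baseline scan on or after day 42 meets the condition. SD on day 38 followed by PD near day 84 satisfies it. Only patients with no scan after the early one lose SD.
- Strict: the SD finding itself must fall on or after day 42. Then SD on day 38 followed by PD near day 84 is not SD.

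**3. Size, strict reading.**

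Inputs from protocol 12.2.1: median PFS 3.9 months (eribulin) and 5.6 months (combination), with 384 patients, so 192 per arm.

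Assumptions: exponential PFS, 30.4375 days per month, first-scan days uniform over 35–49, second scan at day 84.

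S(t) = exp(−ln 2 × t / (median × 30.4375)). The share progression-free at an early scan but with an event by day 84 is about (7/15) × [S(38) − S(84)], day 38 being the middle of days 35–41.

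- Eribulin: S(38) = 0.801, S(84) = 0.612; (7/15) × 0.189 = 8.8%, about 17 of 192.
- Combination: S(38) = 0.857, S(84) = 0.711; (7/15) × 0.146 = 6.8%, about 13 of 192.

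These are ceilings, because confirmed responders have not been removed. The documents give no scan-day distribution, so the range matters:

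| Share of first scans before day 42 | Eribulin | Combination |
|---|---|---|
| 18% | 3.4% | 2.6% |
| 46.7% (uniform) | 8.8% | 6.8% |
| 78% | 14.7% | 11.4% |

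**4. Size, literal reading.** Assume that 5–25% of the patients in step 3 have no later scan (the documents give no figure). With uniform scan days:

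- Eribulin: 0.05 × 8.8% = 0.4% to 0.25 × 8.8% = 2.2%, or 0.8 to 4.2 patients.
- Combination: 0.05 × 6.8% = 0.3% to 0.25 × 6.8% = 1.7%, or 0.7 to 3.3 patients.

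At the 78% extreme with a 25% share, these become 3.7% and 2.8%.

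**5. Contrast between arms.** With uniform timing, 78.3% (eribulin) and 84.3% (combination) are progression-free at the first scan, a difference of 6.0 points. Removing the strict-reading losses gives 69.5% and 77.5%, a difference of 8.0 points. This 2-point movement comes entirely from the assumed difference in progression rates.

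**6. What is untouched.** SD, PD and NE are all non-response, so ORR does not move. CBR requires SD for at least 6 months, well past either cut-off. PFS, OS and the alpha allocation do not use the rule.

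**The case against.** The strongest reply is that the texts can be reconciled. The NE sentence names the 6-week assessment, and that visit carries ±7 days. The 42 days may be only the nominal visit day, with the SAP spelling out the window. Protocol 12.1 says the SAP will expand on the protocol's methods. This is a fair account of what was probably meant, but it is not what the sentence says: it prints a day count followed by a lower bound, with no window.

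Second, the quoted condition asks for at least one scan on or after day 42, not for SD to be seen then, so a patient with SD and then PD at the second scan meets it. That stands, and it is why the literal figures come first. Table 17 in protocol Appendix 3 does not settle the matter: it invokes a minimum SD duration, but its rows start from CR, PR or NE and none covers SD followed by PD.

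Third, neither DCR definition states a 42-day minimum, so an effect on DCR is conditional. That also stands. The protocol gives no other SD minimum and the SAP builds DCR from best response, so the link is plausible but unstated.

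A reader might go further and infer that DCR in the Overall Population is biased between arms, with the treatment difference overstated by about 2 points. The documents do not support that. One rule and one schedule from randomization apply to both arms, so the direct effect is a lower rate in each. Any change in the contrast needs the strict reading, an assumed spread of scan days and truly different progression rates. Calling it overstated also presumes that day 35 is the correct threshold. Nor is it established that the same patient would appear as SD in one regulatory report and PD in another, because no detailed analysis plan for the Overall Population is among the documents.

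**Conclusion.** The inconsistency is real and minor. The protocol's cut-off excludes part of its own permitted scan window, leaves patients with a single early on-time SD scan without a clear category, and conflicts with the SAP's 35-day floor in the 3rd line+ population without being listed as a change. For the Overall Population, the supplied documents leave day 42 in place.

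The effect is confined to the best-response table and, if the minimum feeds it, DCR, which is outside Type I error control. The literal-reading size of about 0.3–2.2% per arm rests on uniform scan days and an assumed 5–25% without a later scan. The strict-reading figure of about 7–9% is a ceiling under uniform scan days with responders left in. Neither is an estimate of bias between arms.

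**What to change.** - In protocol 12.2.7.4, replace the 42-day minimum with at least 35 days from randomization (6 weeks minus the 7-day window), for both populations.
- Word the NE sentence with the same cut-off, so that every patient falls in one category.
- State whether the minimum applies to DCR, and reconcile SAP 8.4.4, which accepts SD of any length, with the 35-day requirement in Appendix 14.5.
- List the change in SAP section 12.

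The cost is a few lines of text. No new data, visits or sample size are needed, and no confirmatory analysis changes.
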